8.5.1.3 Part 2 – Overall Survival

In Part 2, the primary analysis will test for the superiority of varlitinib-containing treatment arm relative to the placebo-containing arm, as assessed by OS.

The primary analysis of OS will be performed after the 247th documented OS event. OS will be analyzed using the methods described in [Section 8.5.1.2](#) for PFS.

Patients whose data contributed to the Part 1 analysis will not contribute to the Part 2 analysis.

8.5.2 Secondary Endpoints

8.5.2.1 Efficacy Endpoints

Progression-free survival based on site assessments

In all study parts, PFS based on the site review of radiological data is a secondary endpoint. PFS based on site data will be analyzed using the same model and methodology as described in [Section 8.5.1.2](#) for PFS based on ICR.

Further details will be provided in the SAP.

Duration of Response

The DoR will not be formally analyzed. Duration of response will be listed and presented using KM curves. Descriptive statistics, based on the KM estimates, will be presented by treatment group.

Overall Survival (Part 1)

In Part 1, OS will be analyzed using the methods described in [Section 8.5.1.2](#) for PFS. OS will be analyzed twice. The initial analysis of OS will be performed at the time of the primary analysis of ORR and PFS. Due to the number of OS events expected at the time of the first analysis, this initial analysis of OS will be considered exploratory only. Although a p-value may be presented, for the purpose of marketing authorization, no claims of statistical significance will be based on the initial analysis. A further OS update analysis is performed when approximately 95 OS events have occurred. To support marketing authorization, for the purpose of type I error control across the two analyses of OS, the OS update analysis will be considered the primary analysis of OS in the study.

Disease Control Rate

Disease control rate will be analyzed using a stratified exact binomial test¹⁶ that extends Fisher's Exact test to more than 1 stratum. The analysis will be stratified by primary tumor location (GB/Non-GB). The 2-sided p-value will be obtained by doubling the 1-sided p-value.

The conditional maximum likelihood estimate of the odds ratio will be presented together with its exact 2-sided 95% confidence limit, which excludes one if and only if the stratified exact binomial test is significant at a 2-sided 5% level. Corresponding significance levels and CIs will be calculated using tests performed at a 1-sided 10% level. The 1-sided p-value will also be presented.

To test for heterogeneity across strata, the exact test of Zelen will be performed testing whether the treatment effect differs between the 2 strata included in the primary analysis.

Tumor Size

The percentage change from baseline in tumor size at Week 12 ($\% \Delta TS_{Wk12}$) is a secondary endpoint for Part 1. Tumor size is not considered to be a key secondary endpoint; for the purpose of marketing authorization no statistical claims will be based on tumor size.

Tumor size will be presented graphically using waterfall plots for each treatment arm, presenting each patient's Week 12 percentage change in tumor size as a separate bar with the bars ordered from the largest increase to the largest decrease. Reference lines at the +20% and -30% change in tumor size levels will be added to the plots, which correspond with the definitions of disease progression and PR, respectively. In these waterfall plots, the patients whose Week 12 percentage change in tumor size is based on an imputation will be clearly shown. The 2 treatment arms will be plotted separately, but presented side-by-side on a single page.

Waterfall plots of the best percentage change from baseline will also be presented, as described above for the Week 12 percentage change from baseline.

Tumor size will also be used to help evaluate the exploratory objectives of exploring relationships between baseline biomarker levels and clinical outcomes (e.g., baseline HER2 status and clinical outcome, and other HER family statuses and clinical outcomes).

In line with the exploratory objectives of the study, the statistical analysis of tumor size in Part 1 will be also be used to help evaluate the role of HER family expression levels status as a predictor of benefit to varlitinib. If a relationship is found between biomarker(s) expression and clinical outcomes in Part 1 of the study, the biomarker(s) could be prospectively evaluated in Part 2 of the study.

These analyses will be exploratory, and may be driven by the data observed, and specifically the prevalence of the HER family sub-groups of interest. However, the analysis principles to be followed are outlined below.

1. ASLAN will create and document a list of the key biomarkers of interest, based upon the biological plausibility of predictivity for clinical outcomes. The list will be limited to those biomarkers, or combinations of biomarkers for which a scientific hypothesis exists. These will represent the biomarkers that will be used

- to assess the listed exploratory objectives, providing that there is sufficient prevalence of that biomarker in the study population.
2. For each biomarker of interest, each patient's baseline biomarker status will be independently evaluated blinded to study treatment and clinical outcome
 3. For each biomarker sub-group, or combination of biomarkers identified on the prospectively defined list (step 1), if at least 15 patients in the EFR population are determined to be expressors, then the role of that biomarker as a predictor of clinical outcome (tumor size) will be evaluated as described below.

For each biomarker of interest (or combination of biomarkers), the absolute values at baseline and Week 12, along with the percentage change from baseline target lesion size at Week 12 will be summarized using descriptive statistics and presented by treatment arm and baseline biomarker status.

The number and percentage of patients in each treatment arm whose Week 12 data is imputed will also be presented (split by biomarker sub-group).

The effect of varlitinib on percentage change in tumor size will be estimated from an analysis of covariance (ANCOVA) model fitting the Week 12 percentage change from baseline as the response variable, and treatment, primary tumor location (GB/Non-GB), baseline biomarker status (positive or negative), the interaction treatment x baseline biomarker status, baseline tumor size, and the time from the baseline scan to randomization as covariates.

The significance of the interaction term will be evaluated at the 1-sided 10% level to determine whether there is evidence of a treatment by biomarker interaction. Regardless of the significance of the interaction term, the number of patients, unadjusted mean and adjusted least squares (LS) means for each treatment arm will be presented for each level of biomarker status factor (positive or negative), together with the difference in adjusted LS means between treatment arms for each level of the biomarker status factor and corresponding p-value and 80% and 95% CIs for the difference.

If the interaction term is not significant at the 1-sided 10% level, the number of patients, unadjusted mean and adjusted least squares (LS) means for each treatment arm will also be presented together with the difference in adjusted LS means between treatment arms and corresponding p-value and 80% and 95% CIs for the difference.

If, at blind review, it is judged that the data do not adequately follow a normal distribution assumption, then a log-transformation may be used. Specifically in place of percent change in Week 12 value the ANCOVA model will use \log_e (Week 12/baseline). In this situation, the ratio of the geometric LS means corresponding CI and p-value will be presented.

As a sensitivity analysis, a nonparametric analysis will be performed. The Hodges Lehmann estimate of the median difference and corresponding 80% CI will be derived and presented. The median percentage change and range will be presented for each

treatment arm, together with the number of patients and percentage of patients in each treatment arm whose Week 12 data is imputed in the nonparametric analysis.

For all biomarkers of interest (step 1), waterfall plots color-coded by baseline biomarker status will be produced.

Note, due to the differing timeframes of the endpoints being available for analysis, the above statistical analyses of the biomarker data will be reported outside of the study CSR.

8.5.2.2 Safety Data Analysis

For each study part, safety data will be assessed for the safety population.

All AE data will be listed along with information regarding initial study dose, dose at onset, onset time (study day), duration, severity, and relationship to study treatment.

Treatment emergent AEs (TEAEs) are defined as AEs with an onset date on or after the start of treatment. The following summaries will be produced, by treatment group and overall for all TEAEs:

- An overview table of the incidence of TEAEs, grade 3+ TEAEs, SAEs, TEAEs leading to treatment discontinuation and TEAEs leading to death, by treatment arm and overall. For each summary category, the results will be shown overall (regardless of causality), and for the incidence of causally-related TEAEs. For example, the overall incidence of TEAEs will be presented, as well as the incidence of TEAEs related to randomized therapy, the incidence of TEAEs related to capecitabine and the incidence TEAEs related to both randomized therapy and capecitabine.
- Summary of TEAEs by system organ class and preferred term: Both the number and percentage of patients in each category (patient-level summary) and the number of episodes (episode-level summary). This summary table will be repeated for TEAEs attributed as *causally related to randomized therapy* (varlitinib or placebo)
- Summary of TEAEs occurring in at least 10% of patients, sorted in descending order of frequency (i.e., most frequent event shown first). The order of frequency will be determined by the most frequent preferred term across both arms, regardless of CTC grade. For each event, the results will be presented for all CTC grades, and also split by grade 1-2, and grade 3+.
- Summary of TEAEs attributed as *causally related to randomized therapy* occurring in at least 10% of patients, sorted in descending order of frequency (i.e., most frequent event shown first). The order of frequency will be determined by the most frequent preferred term across both arms. For each event, the results will be presented for all CTC grades, and also split by grade 1-2, and grade 3+.

- Summary of CTC grade 3 and above TEAEs sorted in descending order of frequency (i.e., most frequent event shown first). The order of frequency will be determined by the most frequent preferred term across both arms.
- A summary of CTC grade 3 and above TEAEs attributed as *causally related to randomized* therapy sorted in descending order of frequency (i.e., most frequent event shown first). The order of frequency will be determined by the most frequent preferred term across both arms.
- Summary of SAEs by preferred term
- Summary of SAEs attributed as *causally related to randomized* therapy, sorted by preferred term
- Categorical Analysis of ECG findings (See [Section 8.5.2.3](#))

Additionally, the following will be listed:

- AEs with outcome of death along with the date of onset, dosing day, dose at onset, treatment status at onset (pre-treatment, ongoing or post-treatment) and Investigator's assessment of severity and relationship to study drug
- All SAEs along with the date of onset, dosing day, dose at onset, treatment status at onset (pre-treatment, ongoing or post-treatment), date of resolution (if AE is resolved), Investigator's assessment of severity and relationship to study drug
- AEs leading to discontinuation of study medication, listed along with the date of onset, dosing day, dose at onset, treatment status at onset (pre-treatment, ongoing or post-treatment) and Investigator's assessment of severity and relationship to study drug

If an AE is reported more than once during the study period, the greatest severity and the worst-case attribution will be presented in summary tables. Any AEs commencing > 28 days after discontinuation of study treatment will not be included in the tabulations of AE data.

All clinical laboratory data (clinical chemistry, hematology and urinalysis data), vital signs and ECG data will be listed. Data tabulations and graphical displays of clinical laboratory data (clinical chemistry, hematology, and urinalysis data), vital signs and ECG data, will include all assessments from screening up to (and including) 28 days after discontinuation of study treatment. In addition, all data measured on a continuous scale (except respiration rate and pulse) will be displayed graphically as described below:

Safety lead-in:

- Patient profile plots of laboratory data over time, including reference lines at the LLN and ULN. Any dose reductions will be indicated on the plots using a change in line-type.
- Patient profile plots of the change from baseline over time, including a horizontal reference line at zero. Any dose reductions will be indicated on the plots using a change in line-type.

Parts 1 and 2:

- Box plots of laboratory data over time, by treatment, including reference lines at the LLN and ULN
- Box plots of the change from baseline over time, by treatment, including a horizontal reference line at zero

To enable assessment of the potential for drug-induced liver injury, for all study parts the following outputs will be produced:

- A scatter plot of maximum on-treatment ALT versus maximum on-treatment total bilirubin (x-axis), both expressed as multiples of the upper limit of normal (ULN), including reference lines at $3 \times \text{ULN}$ for ALT, and $2 \times \text{ULN}$ for total bilirubin. For each patient, the maximum ALT and maximum total bilirubin may occur at different visits
- A scatter plot of maximum on-treatment AST versus maximum on-treatment total bilirubin (x-axis), both expressed as multiples of the upper limit of normal (ULN), including reference lines at $3 \times \text{ULN}$ for AST, and $2 \times \text{ULN}$ for total bilirubin. For each patient, the maximum AST and maximum total bilirubin may occur at different visits.

In the event that the scatter plots of ALT or AST against bilirubin identify any potential Hy's law cases (patients with either both $\text{ALT} > 3 \times \text{ULN}$ and $\text{total bilirubin} > 2 \times \text{ULN}$, or both $\text{AST} > 3 \times \text{ULN}$ and $\text{total bilirubin} > 2 \times \text{ULN}$), profile plots over time will be produced for these patient's liver function tests (ALT, AST, ALP, and total bilirubin), expressed in multiples of the ULN, showing all 4 LFT parameters on the same plot.

Physical examination data will be listed.

To further assess the tolerability of varlitinib, exposure and dose intensity will be listed and summarized by treatment arm. Further details will be provided in the study SAP.

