Treatment:	
Safety lead-in Per oral (PO) varlitinib 300 mg BID, every day. PO capecitabine 1000 mg/m² BID from Day 1 to Day 14 followed by 7-day of rest period, every 21 days. Treatment will continue for a minimum of 14 days, during which dose adjustment is not allowed. Dose adjustment and interruption is allowed from day 15 onwards. Treatment will continue in 21-day cycles until disease progression, development of unacceptable toxicity, withdrawal of consent, or death.
 
Part 1 and Part 2 PO varlitinib 300 mg (if assessed as safe in Safety lead-in) or matching placebo, both BID, every day PO capecitabine 1000 mg/m² BID from Day 1 to Day 14 followed by a 7-day of rest period, every 21 days Treatment will continue until unacceptable toxicity, disease progression, withdrawal of consent or death. Dose modification will be permitted where required according to protocol.

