5.4.6 Procedures for Randomization

Patients must not be randomized unless all eligibility criteria have been met. For Part 1 only, this includes receiving eligibility confirmation from the ICR.

Patients who satisfy all the entry criteria will be centrally assigned to study treatment by the RTSM, according to the randomization scheme generated by the designated CRO. Patients will be randomized in a 1:1 ratio to either varlitinib or placebo, both on a background of capecitabine (n=120 for Part 1 and n=350 for Part 2). The randomization scheme will be stratified by the following 2 covariates:

- Geographical region - US or ROW
- Primary tumor location – gallbladder (GB) or non-GB

The actual treatment given to patients will be determined by the randomization scheme in RTSM. The randomization scheme will be produced using SAS® version 9.4, which incorporates a standard procedure for generating randomization numbers. One randomization list will be produced containing sufficient random numbers for each of the 4 randomization strata. A blocked randomization will be generated and all centers will use the same list in order to minimize any imbalance in the number of patients assigned to each treatment group.

The dose and regimen of randomized therapy to be administered is as follows:

- Varlitinib 300 mg BID, every day
- Placebo BID, every day

Patients in both arms will receive background chemotherapy with capecitabine 1000 mg/m² BID, Day 1 to 14, followed by a 7-day rest period (21-day cycle).

Patients will be identified to the Centralized Randomization Center using site number, screening number, randomization number, gender, and date of birth. Patients will be randomized strictly sequentially within each stratum, as patients are eligible for randomization. The RTSM will inform the Investigator of the Kit ID number to be allocated to the patient at each dispensing visit via electronic data capture (EDC).

Study medication should only be dispensed to each randomized patient at the Cycle 1 Day 1 visit. It is allowed to randomize patient up to 24 hours prior to first dose. The first dose of study medication must only be administered in the morning of Cycle 1 Day 1 after pre-dose assessment (e.g., safety laboratory sampling, electrocardiogram [ECG], PK sampling) are completed. The day on which a patient takes the first dose of study medication will be considered Cycle 1 Day 1.

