8.2.2 Part 1 Sample Size

Part 1 is designed with co-primary endpoints ORR and PFS. In order to maintain an overall, 1-sided 10% type I error rate for Part 1, a Hochberg procedure¹⁵ will be used, such that the study will be deemed to have met its primary objective if either endpoint is significant at the 1-sided 5% level or if both endpoints are significant at the 1-sided 10% significance level.

One hundred and twenty patients provide approximately 80% power to detect a true difference of 17% in response rate, based on a 1-sided 5% significance level and assuming 10% response rate for the placebo group and a 27% response rate for varlitinib. To ensure the adequate data are available to evaluate the effects of varlitinib on both co-primary endpoints, the DCO for the primary analysis will be the later of 3 months after last patient in and when 70% of patients (84 patients) have experienced a PFS event. Based on a minimum of 84 PFS events at the time of the primary analysis, the study would have a minimum of 80% power to detect a true HR of 0.58 for PFS based on a 1-sided 5% significance level.

Furthermore, if the primary objective of the study is met, the following approach to type I error control will be applied in order to support marketing approval:

- The overall type I error rate for marketing approval will be controlled at the two-sided 5% level, using a Hochberg procedure
- Using this approach, statistical significance may be claimed if *either* ORR or PFS is significant at the two-sided 2.5% significance level or if *both* ORR and PFS are significant at the two-sided 5% significance level.

One hundred and twenty patients provide approximately 80% power to detect a true difference of 20% in response rate, based on a 2-sided 5% significance level and assuming 10% response rate for the placebo group and a 30% response rate for varlitinib.

A total of 84 PFS events provides 80% power to detect a true HR of 0.54, based on a two-sided 5% significance level. Assuming a 8-month non-linear recruitment period, a 2.67 month median PFS for capecitabine alone, and a true HR of 0.54, it is estimated that the DCO for the primary analysis of Part 1 will occur approximately 12 months after the first patient is randomized into the study (first patient in).

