### 7.7.1 Assessment of Adverse Events

All AE data will be listed along with information regarding initial study dose, dose at onset, onset time, duration, severity, and relationship to study treatment.

Treatment emergent AEs (TEAEs) are defined as AEs with an onset date on or after the start of treatment. The following summaries will be produced, by treatment group and overall for all TEAEs:

- An overview table of the incidence of TEAEs, grade 3+ TEAEs, SAEs, TEAEs leading to treatment discontinuation and TEAEs leading to death, by treatment arm and overall. For each summary category, the results will be shown overall (regardless of causality), and for the incidence of causally related TEAEs. For example, the overall incidence of TEAEs will be presented, as well as the incidence of TEAEs related to randomized therapy, the incidence of TEAEs related to capecitabine and the incidence TEAEs related to both randomized therapy and capecitabine.
- Summary of TEAEs by system organ class (SOC) and preferred term: Both the number and percentage of subjects in each category (subject-level summary) and the number of episodes (episode-level summary). This summary table will be repeated for TEAEs attributed as *causally related to randomized therapy* (varlitinib or placebo)
- Summary of TEAEs occurring in at least 10% of subjects, sorted in descending order of frequency (i.e. most frequent event shown first). The order of frequency will be determined by the most frequent preferred term across both arms, regardless of CTC grade. For each event, the results will be presented for all CTC grades, and also split by grade 1-2, and grade 3+.
- Summary of TEAEs attributed as *causally related to randomized therapy* occurring in at least 10% of subjects, sorted in descending order of frequency (i.e. most frequent event shown first). The order of frequency will be determined by the most

frequent preferred term across both arms. For each event, the results will be presented for all CTC grades, and also split by grade 1-2, and grade 3+.

- Summary of CTC grade 3 and above TEAEs sorted in descending order of frequency (i.e. most frequent event shown first). The order of frequency will be determined by the most frequent preferred term across both arms.

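### No planned adverse-event table accounts for unequal treatment time, so for events whose risk continues on treatment a PFS benefit can itself look like extra toxicity

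*Protocol*

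**What the plan says.** **Measure.** Protocol 8.5.2.2 sets the system organ class and preferred term tables as "Both the number and percentage of patients in each category (patient-level summary) and the number of episodes (episode-level summary". SAP 7.7.1 repeats this: "Both the number and percentage of subjects in each category (subject-level summary) and the number of episodes (episode-level summary". The remaining AE tables (overview, grade 3 and above, serious, occurring in at least 10%) are also incidence summaries by arm. The SAP table list (14.3.2.1 to 14.3.2.9) has no rate per patient-time, no time-to-first-event or cumulative-incidence analysis, and no table limited to a common period.

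**Window.** An AE counts as treatment-emergent from the start of treatment. The other end is set by "Any AEs commencing > 28 days after discontinuation of study treatment will not be included in the tabulations of AE data".

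**Treatment length.** It is not fixed. The synopsis says for Parts 1 and 2: "Treatment will continue until unacceptable toxicity, disease progression, withdrawal of consent or death".

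**Exposure.** Days of exposure and dose intensity are summarised by arm in their own tables (14.3.1.1 and 14.3.1.2; SAP 3.2.2 and 7.7.5). No AE summary uses them as a denominator.

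**Planned effect.** Part 1 randomizes 1:1 and is planned around "a 2.67 month median PFS for capecitabine alone, and a true HR of 0.54".

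**The concern.** A patient's counting window is as long as that patient's treatment plus 28 days. If treatment time differs between the arms, so does the time in which an AE can be recorded, and a crude percentage mixes the AE rate with the length of observation. Episode counts do the same.

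The distortion can go either way. If varlitinib delays progression, an AE with the same underlying rate in both arms can look more common on varlitinib. If varlitinib is stopped early for toxicity, the shorter window can conceal a higher rate.

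Safety is a secondary objective of both randomized parts, and protocol 5.2 says the study is meant to support a decision on marketing approval. A reader of the planned output could see that exposure differs, but no planned table would show how much of an AE difference that explains.

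**Working it through.** **1. The plan's own figure.** Protocol 8.2.2 states: "A total of 84 PFS events provides 80% power to detect a true HR of 0.54, based on a two-sided 5% significance level". By Schoenfeld's formula with 1:1 allocation, events needed = 4 × (1.960 + 0.842)² / (ln 0.54)² = 82.7, so 83. Power with 84 events = Φ(√84 / 2 × 0.616 − 1.960) = Φ(0.864) = 80.6%. The figure is reproduced.

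**2. Treatment time if it follows PFS.** Assume exponential PFS and stopping only at progression.
- Control progression hazard: ln 2 / 2.67 = 0.260 per month, mean 3.85 months.
- Varlitinib: 0.54 × 0.260 = 0.140 per month, median 2.67 / 0.54 = 4.94 months, mean 7.13 months.
- Ratio of means 1.85. With the 28-day tail (0.92 month): 8.05 / 4.77 = 1.69.

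**3. Crude incidence with complete follow-up.** Take the same AE hazard h = 0.1 per month in both arms (illustrative; not in the documents). With progression hazard m, P(AE) = 1 − exp(−0.92h) × m / (m + h).
- Control: 1 − 0.912 × 0.260 / 0.360 = 34%.
- Varlitinib: 1 − 0.912 × 0.140 / 0.240 = 47%.

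**4. The same example at the planned cut-off.** Protocol 8.2.2 expects that the "DCO for the primary analysis of Part 1 will occur approximately 12 months after the first patient is randomized into the study", after 8 months of recruitment described only as non-linear. Time at risk becomes the smaller of (PFS time + 0.92) and (12 − entry time). Two recruitment shapes were simulated: the quadratic form that the synopsis gives for Part 2, scaled to 8 months, and a linear one.

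| Follow-up | Control | Varlitinib | Excess | Time-at-risk ratio |
|---|---|---|---|---|
| 12-month cut-off, quadratic | 30% | 36% | +6 points | 1.25 |
| 12-month cut-off, linear | 31% | 39% | +7 points | 1.30 |
| Complete | 34% | 47% | +13 points | 1.69 |

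Quadratic recruitment gives 83.8 expected PFS events at month 12, in line with the plan's 84.

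**5. Other AE frequencies, equal hazard in both arms.** The low end is the 12-month cut-off (quadratic) with the 28-day tail. The high end is complete follow-up counting on-treatment time only.

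| Control | Varlitinib |
|---|---|
| 10% | 12-17% |
| 20% | 24-32% |
| 30% | 36-44% |
| 50% | 58-65% |

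**6. When the excess goes away.**
- AE risk confined to the first 6 weeks: 20% becomes 20.2%, and 50% becomes 50.3%.
- Extra stopping on varlitinib for toxicity at 0.05 per month: the 12-month quadratic result falls to 30% against 33%.
- Extra stopping at 0.260 − 0.140 = 0.12 per month: no excess. That means 0.12 / 0.26 = 46% of varlitinib patients stopping for toxicity before progression. More than that reverses the sign.

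**7. What the added tables would show.** With equal constant hazards the exposure-adjusted rate is 0.1 per month in each arm, so the rate ratio is 1.00 by construction. Crude percentages within the first 12 weeks are about 21% and 22%, a gap of about 1 point.

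**The case against.** The strongest reply is that the AE tables are descriptive. No between-arm AE test is planned, and the crude percentage correctly answers a real question: what share of patients has the event over a course of treatment given until progression. That stands. It is why the crude tables should stay, and why adjusted rates should not become the sole basis for safety statements, since that would only swap one estimand for another.

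Second, the information is not lost. AE listings carry onset and dose at onset, exposure is summarised by arm, and laboratory data are plotted over time by arm. This also stands, but it lets a reader notice an imbalance without correcting for it.

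Third, the inputs fit imperfectly. Treatment stops at investigator-assessed progression (protocol 5.4.1), whereas the planned PFS effect concerns central review. AE reporting ends early if new anti-tumor therapy starts (protocol 7.1.1.1 and 7.1.1.2), so not every patient has the full 28-day tail. The AE hazard is an assumption. These points limit the precision of the figures, not the mechanism.

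Two stronger readings are tempting, and the documents support neither.
- A reader might infer that longer treatment will by itself always create a false excess on varlitinib. That needs a risk that continues on treatment and a treatment time that tracks PFS. Protocol 3.2.2 describes the onset of diarrhea, nausea and vomiting as variable, which makes a continuing risk plausible but does not establish it.
- A reader might take 34% against 47% as the expected Part 1 result. That needs unlimited follow-up. At the plan's own cut-off the excess is about half as large.

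**Conclusion.** The point holds in conditional form. Nothing planned in either document corrects an AE comparison for unequal time at risk. For AEs whose risk continues on treatment, a PFS benefit can by itself produce an apparent excess on varlitinib, and early toxicity stops can mask a true one.

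In the illustrative Part 1 example the artefact is +6 to +7 points at the 12-month cut-off. It could move towards +13 points in later reports, since SAP 6.4.2 allows Part 1 safety data to keep accruing. It is near zero for AEs confined to the first weeks.

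The size rests on exponential PFS at the planned hazard ratio, treatment to progression, a constant equal AE hazard of 0.1 per month and an assumed recruitment shape. The gap in the tables affects both randomized parts. The figures apply to Part 1 only, because no PFS hazard ratio is given for Part 2.

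**What to change.** Keep the crude tables. For all, grade 3 and above, serious and common (at least 10%) treatment-emergent AEs, add to SAP 7.7.1 and the table list:

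1. The exposure-adjusted incidence rate of first events by arm, with the rate ratio and confidence interval. Person-time runs from first dose to the first event or 28 days after the last dose, whichever is earlier, and is cut at the data cut-off.
2. The crude percentage within a common early window, the first 12 weeks.

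State that between-arm safety statements will be made with these read alongside the crude tables, and settle this before unblinding so that the choice cannot depend on the AE results.

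The cost is extra output. Dosing dates and AE onset are already collected, exposure is already derived, and no efficacy analysis changes. The rate assumes a roughly constant hazard, which is an approximation; the early-window table does not need that assumption and offsets it.
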